1. VERSION HISTORY

Table 1. Summary of Changes

Version/ Date	Associated Protocol Amendment	Rationale	Specific Changes
3 28 Feb 2025	Final Protocol Amendment 4, 11 Mar 2024 PACL 11, 19 Apr 2024	Hyperlinking updates	
Section 2: Updated section numbers
 
Section 3.2.1: Updated hyperlinking.

2 04 Oct 2024	Final Protocol Amendment 4, 11 Mar 2024 PACL 11, 19 Apr 2024	Removal of ECG and palatability as endpoints. Additional clarifications, definitions, and outputs required.	
Section 2: Edited for clarity. Removed palatability.
 
Section 2.2: Removed ECG from the primary endpoints. Removed palatability objective and endpoint. Added treatment duration.
 
Section 3.1: Removed ECG from the primary endpoints.
 
Section 3.1.3: Removed the definition and convention of ECG.
 
Section 3.1.3.2: Added Oxygen saturation (SpO₂) to the vital sign endpoints and removed the specifications of post- baseline days.
 
Section 3.2: Removed the statements of efficacy and safety endpoints.
 
Section 3.3: Added description of ECG data.
 
Section 3.4: Removed palatability.
 
Section 3.4.1: Edited for clarity.
 
Section 3.4.2: Added duration of signs and symptoms.
 
Section 3.5: Edited for clarity.
 
Section 5.2: Edited for clarity.
 
Section 5.3: Added clarifications of viral loadlisting.

			
Section 6.1.3: Removed analyses and summaries of ECG.
 
Section 6.1.3.2: Removed the summary of vital signs by categorial criteria and clarified output of SpO₂.
 
Section 6.2: Removed the statements on efficacy and safety endpoints.
 
Section 6.2.1: Added clarifications of nominal time.
 
Section 6.4: Removed palatability.
 
Section 6.4.1: Added more analyses on viral load.
 
Section 6.4.2: Added more analyses on RSV signs and symptoms.
 
Section 6.6.1: Added more analyses of baseline characteristics.
 
Section 6.6.4: Removed the summary of maternal RSV vaccine.
 
Appendix 1: Removed the categories for ECG and vital signs.
 
Appendix 2: Updated abbreviations.

1 30 Oct 2023	Final Protocol Amendment 2, 13 Sept 2023 PACL 3 20 Sept 2023	N/A	N/A

2. INTRODUCTION

This statistical analysis plan (SAP) provides the detailed methodology for summary and statistical analyses of the data collected in Study C5241009.

Sisunatovir (PF-07923568, formerly RV521) is a potent inhibitor of respiratory syncytial virus (RSV) F protein mediated cell-to-cell fusion that is currently being investigated in participants with RSV LRTI.

The purpose of this study is to establish safety, tolerability, PK and guidance for dosing of sisunatovir in a pediatric population (1 day up to 60 months of age) with RSV-LRTI for further clinical development of sisunatovir. This study will provide additional safety, tolerability and PK data at ages previously evaluated in C5241003 to inform dose selection

PFIZER CONFIDENTIAL

DMB02-GSOP-RF02 8.0 Statistical Analysis Plan Template

TMF Doc ID: 98.03

Page 5 of 20

in future studies and will also provide this data in a broader pediatric population to inform dose selection in future studies.

2.1. Modifications to the Analysis Plan Described in the Protocol

None. There are no changes to the analysis described in the protocol.

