#### Rationale:

The purpose of this study is to establish safety, tolerability, pharmacokinetic (PK) and guidance for dosing of sisunatovir in a pediatric population (1 day to 60 months of age) with RSV-LRTI, for further clinical development of sisunatovir. Palatability assessments will also be conducted to aid in the development of pediatric formulations of sisunatovir.

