| RSV-associated signs and symptoms (collected by HCP)                                       | X               | X                |         | X       | X       | X       |         | X                | 
 
Day 1 collected pre-dose.
 
Collected daily if hospitalized until time of discharge.
 
Collected if participant has an unplanned in person visit between Days CCI to CCI.
 
See Section 8.2.1.
 
   |
| Palatability assessment for oral dispersion through eDiary by parent(s)/legal guardian/HCP |                 | X                | X       | X       | X       |         |         |                  | 
 
Done after each dose.
 
See Appendix 10D in Section 10.10.4. Also see Section 8.2.2.
 
   |
| Explain eDiary   |                 | X                |         |         |         |         |         |                  | 
 
Explain eDiary completion requirements to participant's parent/legal guardian and assist with access to the eDiary (such as downloading the app or issue a provisioned device, if required).
 
  |

PFIZER CONFIDENTIAL

CT02-GSOP Clinical Protocol Template Phase 1 2 3 4 (14 April 2023)

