## 3. OBJECTIVES, ENDPOINTS, AND ESTIMANDS

| Objectives   | Endpoints  | Estimands  |
|--|--|--|
| Primary:
To evaluate the safety and tolerability of sisunatovir compared to placebo in participants with RSV-LRTI. | Primary: 

Incidence of TEAEs.

Incidence of AEs and SAEs leading to discontinuations.

Incidence of clinically significant abnormal laboratory values and vital signs.

 | Primary: 

Not applicable

   |
| Secondary:
To characterize the PK of sisunatovir in participants with RSV-LRTI.                                    | Secondary: 

Plasma concentrations of sisunatovir at steady state (Day CCI or later).

  | Secondary: 

Not applicable

 |
| Tertiary:
To describe the viral load in NP samples over time in participants with RSV-LRTI.                        | Tertiary: 

Viral load measured via RT-qPCR in NP swabs over time (including but not limited to change from baseline at each sampled visit and proportion of

                          | Tertiary: 

Not applicable

  |

| Objectives   | Endpoints  | Estimands  |
|--|--|--|
|  | participants with BLOQ at Day [REDACTED]
[REDACTED]   |  |
| To describe signs and symptoms assessed by HCP over time in participants with RSV-LRTI       | 

Signs and symptoms over time (including but not limited to change from baseline at Day [REDACTED] and proportion of participants with each sign at Day [REDACTED])

 | 

Not Applicable

 |
| To assess the overall palatability of prepared oral dispersion in participants with RSV-LRTI | 

Responses to palatability questionnaire (eg, participant response to medication) at all time points (specified in protocol).

                                       | 

Not applicable

 |

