#### 4.2.3. Rationale for Comparator

There are currently no approved RSV antivirals available, and thus no active control can be proposed as comparator. The comparator for this study is participants receiving placebo. Each cohort evaluated in the study will have participants on placebo. The placebo group is required for assessing the safety, tolerability, and palatability of the study intervention.

All participants (including participants receiving placebo) enrolled in the study will receive the SOC. Participants enrolled in the study while in the outpatient setting may continue in the study if hospitalized at investigator discretion. C5241003 study that completed recruitment, was conducted to characterize the PK profile, safety and virologic response to sisunatovir in RSV-infected hospitalized children aged 1 month - 36 months and included an open-label Part A (1.0, 2.0 and 2.5 mg/kg single dose) and double-blind Part B (CCI [REDACTED]; 2.5 mg/kg, 3.5 mg/kg and 5 mg/kg q12h × 5 days). Initial pediatric dose recommendations for Cohort 1A, 1B, and 1C are based on observed concentrations in Study C5241003 with interpolation of predicted exposures, relative to exposure of CCI mg CCI in adults.

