- Date, start time of preparation and time of each dose administered
- Administrator of the study intervention: Parent(s)/legal guardian OR HCP
- Route of administration: oral or nasogastric tube for each dose administered
- Information on feeding within 30 minutes before and after dosing
- Palatability questionnaire after every dosing

See the IP Manual for instructions on how to prepare the study intervention for administration.

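### SAP 2.1 declares no change from the protocol, but the palatability objective has been removed and its responses have no planned summary

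*SAP*

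**What the plan says.** **Protocol (Amendment 4).**

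- The synopsis rationale, repeated in Section 2.1, gives palatability as a purpose of the study: "Palatability assessments will also be conducted to aid in the development of pediatric formulations of sisunatovir".
- Section 3 has a tertiary objective, "To assess the overall palatability of prepared oral dispersion in participants with RSV-LRTI". Its endpoint is the questionnaire responses at every protocol-specified time point.
- Section 4.2.3 ties palatability to the design: "The placebo group is required for assessing the safety, tolerability, and palatability of the study intervention".
- The schedule of activities (Table 2) has a palatability row with the note "Done after each dose". Section 6.2.1 lists among the eDiary entries "Palatability questionnaire after every dosing".
- Section 9.3.1 commits to descriptive summaries of every endpoint where applicable. Section 9.3.4 leaves the detail of tertiary analyses to the SAP and allows tertiary results to be reported outside the CSR.
- Section 9 allows the SAP to modify the protocol's analyses. It promises a protocol amendment only for major changes to primary endpoints or their analysis.

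**SAP (version 3).**

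- The version history gives, as part of the rationale for version 2, "Removal of ECG and palatability as endpoints". It records palatability as taken out of Sections 2, 2.2, 3.4 and 6.4. Version 3 lists only section-number and hyperlink updates.
- Both versions are tied to Protocol Amendment 4 (11 March 2024) and PACL 11 (19 April 2024).
- Section 2.1, which exists to declare departures from the protocol, says "None. There are no changes to the analysis described in the protocol".

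**The concern.** The two current documents disagree about what the trial sets out to report. The protocol poses a palatability question, collects the answers at each dose, and cites the question among its reasons for giving some children placebo. The SAP, to which the protocol hands the details, has no palatability objective, endpoint definition or output, and its section on modifications says nothing has changed.

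Two things are at stake. If the SAP is followed as written, parents, guardians and staff complete a questionnaire whose palatability answers have no planned use, and a stated objective gets no result. And anyone relying on SAP 2.1 to learn how the analysis differs from the protocol is told that it does not differ, with no reason given anywhere in the SAP for the removal.

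**Working it through.** The plan gives no figure to reproduce. The check is a comparison of current texts, followed by a simple count for scale.

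**1. Side by side.**

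| Item | Protocol Amendment 4 | SAP version 3 |
|---|---|---|
| Study purpose | Palatability named (synopsis; 2.1) | Section 2 gives the purpose without it |
| Objective and endpoint | Tertiary, Section 3 | Absent from the table in 2.2 |
| Endpoint definition | Questionnaire responses | 3.4 covers viral load, signs and symptoms, and one redacted item |
| Analysis | Descriptive (9.3.1), details left to SAP (9.3.4) | 6.4 covers viral load, signs and symptoms, and one redacted item |
| Collection | After each dose (Table 2; 6.2.1) | No summary of the responses |
| Declared change | Not applicable | None (2.1) |

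**2. Could redaction account for the gap?** This is unlikely. The objectives table in SAP 2.2 labels the redacted objective analysed in 6.4.3 as a virological response, and the version history says outright that palatability was removed from 2.2, 3.4 and 6.4.

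**3. Did the protocol drop palatability first?** Not in any text supplied. ECG, removed in the same SAP version, is a useful contrast. It no longer appears among the primary endpoints in Protocol Section 3, and the entry for Amendment 3 in the amendment history gives the thorough QT study as the reason. For ECG the SAP was following the protocol. For palatability the protocol still has the objective, and neither document gives a reason for removing it.

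**4. Is another plan named?** For population PK, Protocol 9.3.3 and SAP 6.2.1 both point to a stand-alone analysis plan and report. Nothing comparable is named for palatability.

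**5. What remains of the per-dose data?** The eDiary instrument is a combined dosing and palatability questionnaire (Protocol 8.2.2 and Appendix 10D). SAP 6.6.5 still lists full, partial and missed syringe draws for each dose and summarises them as compliance by treatment, cohort and age band. Dosing completeness therefore appears to be covered. The child's response to the medicine is not.

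**6. Scale.**

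- Doses per child, from the visible synopsis text (the stated total is redacted): 2 per day × 5 days = 10. With a single dose on Day 1 and dosing into Day 6: 1 + (2 × 4) + 1 = 10.
- Maximum planned evaluable participants: 108.
- Dosing occasions at that maximum: 108 × 10 = 1,080.

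This is an upper planning figure. It assumes that every optional cohort and every repeat is enrolled and that no dose is missed. The schedule describes the assessment as being for the oral dispersion, while nasogastric dosing is allowed, so some occasions may yield no taste response.

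**The case against.** The strongest reply has four parts.

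- **The removal is disclosed.** The SAP's version history states it and lists the sections affected. This stands. A reader might infer concealment or selective reporting, especially because the sponsor is unblinded, but a dated entry in the SAP itself does not support that. What is missing is the reason, and agreement between the version history and Section 2.1.
- **The protocol permits it.** Section 9 lets the SAP modify non-primary analyses without an amendment, and 9.3.4 lets tertiary endpoints be reported apart from the CSR. This also stands. Dropping the endpoint is not a protocol breach, and a separate report remains possible, so it would be wrong to say that the objective can never be answered. But permission to change the analysis does not make a statement of no change accurate, and 9.3.4 still sends the details to the SAP.
- **PACL 11 may explain it.** The letter is later than Amendment 4, so its content cannot be in the protocol text supplied. The amendment history credits some earlier changes, including removal of a tertiary PK endpoint, to such letters. If PACL 11 withdrew palatability, Section 2.1 could be correct against the protocol as then in force. This cannot be settled from the documents. The contradiction is therefore with the supplied protocol text, and it would be too strong to call 2.1 simply false.
- **The forms are still used.** A reader might conclude that some 1,080 questionnaires go unused. They do not: the dosing-completeness part appears to feed the compliance summary. Only the palatability responses lack an output.

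**Conclusion.** The point holds in a limited form. SAP Section 2.1 contradicts Protocol Amendment 4 as supplied: a tertiary objective and its endpoint have been removed, no reason is given, and the palatability responses have no planned output. The removal is neither hidden nor a breach of the protocol.

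The effect is small. It concerns one tertiary descriptive endpoint in a study without hypotheses, and the primary safety and PK analyses are unaffected. It is still worth correcting, because data already being collected could answer a question that the protocol poses and uses to help justify the placebo group.

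The conclusion assumes that the supplied protocol text is the reference for Section 2.1. If PACL 11 withdrew the objective, the remaining defect is that 2.1 does not say so and the protocol text has not been reconciled.

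**What to change.** Choose one of two routes.

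1. **Restore the summary.** Add to SAP Section 6.4 a descriptive table of the palatability responses by treatment, cohort and age band, showing route of administration so that oral and nasogastric doses are not mixed. Put the objective and endpoint back in Sections 2.2 and 3.4. The cost is one table and a few lines of text, with no new data collection.
2. **Declare the removal.** If it is intended, replace the statement in SAP Section 2.1 with the removal, its reason and the letter that authorised it, if there is one. Then reconcile the protocol's objective, placebo rationale and collection text with that decision. The cost is one SAP paragraph and a protocol clarification.

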2.2. Study Objectives, Endpoints, and Estimands

Type	Objective	Endpoint
	Primary:	Primary:
Safety (Section 6.1)	To evaluate the safety and tolerability of sisunatovir compared to placebo in participants with RSV-LRTI.	
 Incidence of TEAEs. Incidence of AEs and SAEs leading to discontinuations. Incidence of clinically significant abnormal laboratory values and vital signs.
	Secondary:	Secondary:
PK (Section 6.2.1)	To characterize the PK of sisunatovir in participants with RSV-LRTI.	
 Plasma concentrations of sisunatovir at steady state (Day [REDACTED] or later).
	Tertiary:	Tertiary:
Other - Virological response (Section 6.4.1)	To describe the viral load in Nasopharyngeal (NP) samples over time in participants with RSV-LRTI.	
 Viral load measured via RT-qPCR in NP swabs over time (including but not limited to change from baseline at each sampled visit and proportion of participants with BLOQ at Day [REDACTED] CCI).
Efficacy (Section 6.4.2)	To describe signs and symptoms assessed by HCP over time in participants with RSV-LRTI	
Signs and symptoms over time (including but not limited to change from baseline at Day [REDACTED] CCI and proportion of participants with each sign at Day [REDACTED] CCI).
 
 CCI [REDACTED]
Other - Virological response (Section 6.4.3)	CCI [REDACTED]	
 CCI [REDACTED] Viral load in NP swabs and RSV signs and symptoms over time in -participants CCI [REDACTED]

There are no estimands for this study.

2.3. Study Design

This study is a randomized, double-blind, sponsor-open, placebo-controlled, multicenter study in RSV-infected outpatient and hospitalized neonates, infants and children, aged 1 day up to 60 months of age with RSV-LRTI; this is a dose finding study to evaluate the PK, safety and tolerability of sisunatovir.

CCI

[figure not shown]

- Cohorts 1 and 2:

[figure not shown]
A: CCI

[figure not shown]
B:

C:

D:

- Cohort 3:

E: CCI

F:

G:

H:

Sisunatovir or placebo will be administered CCI in a CCI ratio, for a period of CCI for all cohorts.

The sample size has been chosen empirically to provide safety and tolerability information and is not based on statistical power calculation.

CCI participants (CCI active, CCI placebo) are planned for each age band so that approximately CCI evaluable participants (CCI per cohort) may be randomized into the study. The number randomized may be increased if Sponsor recommends repeating the dose for an age band (ie, an additional CCI active and CCI placebo may be enrolled in the same age band). This totals to approximately a maximum of 108 evaluable participants (CCI in each age band + CCI additional in each age band if necessary). The sample size for age bands may be reduced to CCI active, CCI placebo) if there are enrollment challenges. The minimum number of participants is approximately CCI evaluable participants (based on CCI participants per age band) as Cohorts 2 (2A, 2B, 2C, 2D) and 3 (3E, 3F, 3B, 3D) are optional in the study. Participants may be replaced at Sponsor discretion. Participants who discontinue from the study for non-safety reasons may be replaced at the sponsor's discretion in collaboration with the Investigator.

3. ENDPOINTS AND BASELINE VARIABLES: DEFINITIONS AND CONVENTIONS

3.1. Primary Endpoint(s)

The primary endpoints are related to safety/tolerability

PFIZER CONFIDENTIAL

DMB02-GSOP-RF02 8.0 Statistical Analysis Plan Template

TMF Doc ID: 98.03

Page 7 of 20

- *Incidence of TEAEs.*
- *Incidence of AEs and SAEs leading to discontinuations.*
- *Incidence of clinically significant abnormal laboratory values and vital signs.*

3.1.1. Incidence of TEAEs

An AE is any untoward medical occurrence in a study participant administered a product or medical device; the event need not necessarily have a causal relationship with the treatment or usage. An AE is considered a Treatment-Emergent Adverse Event (TEAE) if the event started during the effective duration of treatment. All events that start on or after the first dose of study intervention, but before the end of the study will be flagged as TEAEs. The algorithm will not consider any events that started prior to the first dose date.

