| Demographics   | X               |                  |                        |                        |                        |                        |                        |                                 | 

See Section 8.1.1.

   |
| Registration/ randomization  | X               | X                |                        |                        |                        |                        |                        |                                 | 

Randomization allowed on day of screening after completion of all screening assessments.

At registration, participant enrollment number and dose level allocation assigned.

                |
| Medical History and Physical Examination   |                 |                  |                        |                        |                        |                        |                        |                                 |  |

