#### **8.4.1. Time Period and Frequency for Collecting AE and SAE Information**

The time period for actively eliciting and collecting AEs and SAEs ("active collection period") for each participant begins from the time the parent(s)/legal guardian provides informed consent, which is obtained before undergoing any study-related procedure and/or receiving study intervention, through and including a minimum of 28 calendar days, except as indicated below, after the last administration of the study intervention.

Follow-up by the investigator continues throughout the active collection period and until the AE or SAE or its sequelae resolve or stabilize at a level acceptable to the investigator.

When a clinically important AE remains ongoing at the end of the active collection period, follow-up by the investigator continues until the AE or SAE or its sequelae resolve or stabilize at a level acceptable to the investigator and Pfizer concurs with that assessment.

For participants who are screen failures, the active collection period ends when screen failure status is determined.

If the parent(s)/legal guardian withdraws the participant from the study and also withdraws consent for the collection of future information, the active collection period ends when consent is withdrawn.

If a parent(s)/legal guardian permanently discontinues or temporarily discontinues study intervention (because of an AE or SAE, the AE or SAE must be recorded on the CRF and the SAE reported using the CT SAE Report Form/ PSSA.

Investigators are not obligated to actively seek information on AEs or SAEs after the participant has concluded study participation. However, if the investigator learns of any SAE, including a death, at any time after a participant has concluded study participation, and they consider the event to be reasonably related to the study intervention, the investigator must promptly report the SAE to Pfizer via PSSA.

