### 10.3. Appendix 3: Adverse Events: Definitions and Procedures for Recording, Evaluating, Follow-Up, and Reporting

#### 10.3.1. Definition of AE

| AE Definition   |
|---|
| 

• An AE is any untoward medical occurrence in a patient or clinical study participant, temporally associated with the use of study intervention, whether or not considered related to the study intervention.

• Note: An AE can therefore be any unfavorable and unintended sign (including an abnormal laboratory finding), symptom, or disease (new or exacerbated) temporally associated with the use of study intervention.

 |

| Events Meeting the AE Definition  |
|--|
| 

• Any abnormal laboratory test results (hematology, clinical chemistry, or urinalysis) or other safety assessments (eg, ECG, radiological scans, vital sign measurements), including those that worsen from baseline, considered clinically significant in the medical and scientific judgment of the investigator. Any abnormal test results that meet any of the conditions below must be recorded as an AE:

• Is associated with accompanying symptoms.

• Requires additional diagnostic testing or medical/surgical intervention.

• Leads to a change in study dosing (outside of any protocol-specified dose adjustments) or discontinuation from the study, significant additional concomitant drug treatment, or other therapy.

• Exacerbation of a chronic or intermittent preexisting condition, including an increase in either frequency and/or intensity of the condition.

• New condition detected or diagnosed after study intervention administration, even though it may have been present before the start of the study.

• Signs, symptoms, or the clinical sequelae of a suspected drug-drug interaction.

• Signs, symptoms, or the clinical sequelae of a suspected overdose of either study intervention or a concomitant medication. Overdose per se will not be reported as an AE or SAE unless it is an intentional overdose taken with possible suicidal/self-harming intent. Such overdoses should be reported regardless of sequelae.

 |

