#### Events NOT Meeting the AE Definition

- Any clinically significant abnormal laboratory findings or other abnormal safety assessments that are associated with the underlying disease, unless judged by the investigator to be more severe than expected for the participant's condition.
- The disease/disorder being studied or expected progression, signs, or symptoms of the disease/disorder being studied, unless more severe than expected for the participant's condition.
- Medical or surgical procedure (eg, endoscopy, appendectomy): the condition that leads to the procedure is the AE.
- Situations in which an untoward medical occurrence did not occur (social and/or convenience admission to a hospital).
- Anticipated day-to-day fluctuations of preexisting disease(s) or condition(s) present or detected at the start of the study that do not worsen.

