#### Follow Up of AEs and SAEs

- The investigator is obligated to perform or arrange for the conduct of supplemental measurements and/or evaluations, as medically indicated or as requested by the sponsor, to elucidate the nature and/or causality of the AE or SAE as fully as possible. This may include additional laboratory tests or investigations, histopathological examinations, or consultation with other healthcare providers.
- If a participant dies during participation in the study or during a recognized follow-up period, the investigator will provide Pfizer Safety with a copy of any postmortem findings, including histopathology.
- New or updated information will be recorded in the originally submitted documents.
- The investigator will submit any updated SAE data to the sponsor within 24 hours of receipt of the information.

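### The TEAE rule has no clause for an AE that starts between consent and first dose and worsens after dosing, so that worsening can be lost from the first primary endpoint

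*SAP*

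**What the plan says.** SAP 3.1.1 gives the rule in two sentences. The inclusion sentence reads "All events that start on or after the first dose of study intervention, but before the end of the study will be flagged as TEAEs". Next, the exclusion sentence reads "The algorithm will not consider any events that started prior to the first dose date". Neither mentions a change in severity. The protocol names TEAE incidence as a primary endpoint (Section 3) but only expands the abbreviation, so it supplies no other rule.

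Four protocol provisions bear on how the rule works:

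- Collection of AEs "begins from the time the parent(s)/legal guardian provides informed consent" (Section 8.4.1), so AEs with onset before dosing enter the database.
- Among the events that count as AEs, Section 10.3.1 lists "Exacerbation of a chronic or intermittent preexisting condition, including an increase in either frequency and/or intensity of the condition" and also "New condition detected or diagnosed after study intervention administration, even though it may have been present before the start of the study".
- Signs and expected progression of RSV are not AEs "unless more severe than expected for the participant's condition" (Section 10.3.1).
- In follow-up of an AE, "New or updated information will be recorded in the originally submitted documents" (Section 10.3.3).

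SAP 6.1.1 tabulates TEAEs by cohort, age band and treatment.

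**The concern.** A rule based on onset alone is safe only if every worsening on treatment gets its own record with a post-dose onset. The protocol does not say that it does. These children are acutely ill at entry, and an AE that starts after consent may continue through dosing. If the drug aggravates it, that aggravation is part of the tolerability signal the primary endpoint is meant to show, yet it would be tabulated as though nothing had happened. Gastrointestinal events are the natural example. The protocol synopsis names them as the most commonly reported AEs with this drug, and vomiting and diarrhea are not among the RSV signs in Appendix 10A, so the exclusion for expected disease progression would not obviously remove them.

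There is also a smaller drafting problem. The inclusion sentence is anchored on the first dose and the exclusion sentence on the first-dose date.

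**Working it through.** The plan states no figure for this rule, so there is nothing to reproduce. The check is to follow individual cases through the text.

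**Case 1: onset after consent on Day -1, more severe after dosing.** Two ways of recording it are open to the site.

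| Recording | Onset on file | Result under SAP 3.1.1 |
|---|---|---|
| Worsening entered as a separate AE (allowed by Protocol 10.3.1) | after first dose | flagged as TEAE |
| Severity updated on the existing record (Protocol 10.3.3) | Day -1 | not considered |

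The same clinical course gives opposite results, and no text chooses between the two.

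**Case 2: symptom already present before consent, worse after dosing.** It predates AE collection, so there should be no earlier AE record to update. The worsening can be reported as an exacerbation with post-dose onset and flagged. This case is largely covered.

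**Case 3: onset on Day 1, before the dose.** This can happen because AE collection begins at consent and "Randomization allowed on day of screening after completion of all screening assessments" (Table 2). If the anchor is the date, the event is a TEAE. If first dose means the clock time, the event does not meet the inclusion sentence and is not removed by the exclusion sentence. The text leaves it open.

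**Exposed window.** Table 2 puts screening at Day -1 to Day 1. The exclusion sentence therefore reaches only AEs that start after consent and on a date before Day 1, which is roughly one day. A child who consents and is dosed on the same date has no such window if the anchor is the date.

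**Size.** Inputs: a maximum of 108 evaluable participants (SAP 2.3) and 12 named cohorts, 1A-1D, 2A-2D, 3E, 3F, 3B and 3D (SAP 5.2).

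- Average per cohort, both arms together and including any repeat-dose enrollment: 108 / 12 = 9.
- The active:placebo split is redacted, so cell size m is an assumption. One child changing status moves incidence by 100/m points: m = 3 gives 33.3, m = 6 gives 16.7, m = 9 gives 11.1. The last is a whole average cohort, so an average cohort's single-arm cell is smaller than that.
- Pooled over 108, with an assumed active share of 1/2 to 4/5: active n = 54 to 86, so 100/54 = 1.9 down to 100/86 = 1.2 points. Placebo n = 54 to 22, so 1.9 up to 100/22 = 4.5 points.

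These are the effects of a single reclassified child who has no other TEAE in that row. They say nothing about how often it happens.

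**The case against.** The strongest reply is that the protocol already deals with worsening. The general AE definition in Section 10.3.1 covers a sign, symptom or disease whether newly arisen or aggravated, with no restriction to chronic or intermittent conditions. Day-to-day fluctuation is excluded only when it does not worsen. An acute AE that gets worse after dosing can therefore be reported in its own right, and with a post-dose onset it is a TEAE. That stands, and it rules out saying that worsening is always excluded. It does not close the gap, because being reportable is not the same as requiring a new record with a new onset date, and the follow-up text points to the existing record.

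Three further points limit the consequence and also stand. The window is about a day, and most symptoms at entry will predate consent. AEs leading to discontinuation form a separate primary endpoint with no TEAE restriction (SAP 3.1.2 and 6.1.2), and the stopping rules in Protocol 4.1.1 work on AEs and SAEs rather than TEAE flags. The analysis is descriptive, so no error rate or power is affected. Sponsor imputation standards, cited in SAP 5.3, may add detail but are not reproduced.

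A reader might go further and infer that the rule ignores every event with pre-dose onset, or that it misclassifies events in both directions. The documents do not support either. On the date reading, Day 1 pre-dose events are counted, not ignored. False TEAEs on Day 1 arise only on that reading, which only one of the two sentences uses. Counting same-day onsets is also the conservative choice, since it over-counts events and does not hide them.

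**Conclusion.** The concern holds in a limited form. SAP 3.1.1 contains no worsening clause, and the protocol's recording instructions do not guarantee that worsening of an AE begun between consent and first dose receives a post-dose onset. Such worsening can therefore be lost from the first primary endpoint, depending on how the site fills in the record.

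The frequency is unknown and probably low given the short window. The effect of one case is large in a single cohort-by-arm cell and small when pooled. The per-cell figures rest on assumed cell sizes. The completed pediatric study's finding that vomiting made up 3 of the 5 related TEAEs in its single-dose part shows that gastrointestinal events matter, but it gives no information on pre-dose onset or worsening. The mismatch between dose and dose date is an ambiguity to tidy and would not justify a separate point.

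**What to change.** In SAP 3.1.1, add that an AE with onset before first dose which increases in severity after first dose is also treatment-emergent. Implement it through a CRF completion instruction: when severity increases after first dose, enter the worsening as a new AE with its own onset date. The existing inclusion sentence will then pick it up.

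As a secondary edit, use the same anchor in both sentences and keep Day 1 onsets as TEAEs unless the record shows that onset came before the dose.

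The cost is slightly more than one SAP sentence. Dose time is recorded in the eDiary (Protocol 6.2.1), but the documents do not state that AE onset time is collected, and Section 10.3.3 describes one intensity category per AE, with no serial grading. The change therefore needs the site instruction and a small programming change. Recording the worsening as a new entry avoids depending on serial severity fields, and the Day 1 default avoids depending on onset times that may be missing.
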